8.1.3 Washout Intervals

Prohibited medications, treatments, and activities are outlined in the Exclusion Criteria ([Section 5.4](#)). They include:

- LASIK – 12 months prior to Visit 1 and throughout study period
- Ocular surgery – 12 months prior to Visit 1 and throughout study period
- Contact lenses – 30 days prior to Visit 1 and throughout study period
- Punctal Plugs – 3 months prior to Visit 1 and throughout study period
- Nasal spray (TYRVAYA[®]) – 30 days prior to Visit 1 and throughout study period
- Topical ocular cyclosporine (Restasis[®] or CequaTM) – 45 days prior to Visit 1 and throughout study period
- Topical lifitigrast (Xiidra[®]) – 45 days prior to Visit 1 and throughout study period
- Topical Eyedrops – 24 hours prior to Visit 1 and throughout study period
- Unstable medication causing ocular drying or increased lacrimation – 30 days prior to Visit 1 and throughout study period
- Investigational drug or device – 45 days prior to Visit 1 and throughout study period

8.1.4 Procedures for Final Study Entry

Patients must meet all inclusion and none of the exclusion criteria.

8.1.5 Methods for Assignment to Treatment Groups:

At Visit 1, patients who provide written informed consent will be assigned a unique 5-digit screening number, which includes the 2-digit site number plus a unique 3-digit screening number beginning with 001 (eg, 11-001, 11-002, 11-003, etc.). Screening numbers must be assigned in ascending consecutive order.

Prior to Visit 2, the Medical Monitor will review the medical and medication history, screening results and screening eligibility criteria for each patient who enters the run-in period, and confirm the patient's eligibility for the study. If there is a change in medical or medication status between Visits 1 and 2, the Medical Monitor will review and confirm the patient's eligibility for the study prior to randomization at Visit 2 (if possible) or as soon as possible after Visit 2.

At Visit 2, a patient who meets all the eligibility criteria will be randomized to receive treatment with 0.3% SI-614 or placebo in a 1:1 ratio. The Interactive Voice/Web Response System (IVRS/IWRS) will be used to account for the stratification factors.

Patient's will be stratified by the following factors and cut-offs:

1. Average of dryness and ocular discomfort at bedtime assessment for Run-in patient daily diary mean (Day -7 through Day -1).
 - a. ≤ 2.5
 - b. > 2.5
2. Change [REDACTED] in total corneal fluorescein staining at Visit 2
 - a. ≤ 3.5
 - b. > 3.5

Both strata will be entered into the IVRS/IWRS, which will assign the randomization number and the assigned kit number for the patient. The site staff will dispense to the patient the study kit labeled with the corresponding kit number. Both the randomization number and the dispensed study drug kit number will be recorded on the patient's source document and eCRF.

8.2 Concurrent Therapies

The use of any concurrent medication, prescription or OTC, is to be recorded on the patient's source document and corresponding eCRF along with the reason the medication was taken. Concomitant medications that are considered necessary for the patient's welfare, but will not interfere with study assessments and evaluations, will be allowed during the study at the Investigator's discretion.

Use of medications known to cause ocular drying or increased lacrimation (see [Appendix 3](#)) is allowed; however, any use of medications known to cause ocular drying or increased lacrimation must be on a stable dosing regimen for at least 30 days prior to Visit 1, and should remain stable during the study period. A change in the use of a medication known to cause ocular drying or increased lacrimation during the study period will be recorded as a protocol deviation.

Concurrent enrollment in another investigational drug or device study is not permitted.

8.2.1 Prohibited Medications/Treatments

Disallowed medications/treatments during the study are outlined in the Exclusion Criteria ([Section 5.4](#)).

If a specific medication/therapy has the potential to interfere with the treatment effect of the study drug or interpretation of the study results, the Investigator should contact the Medical Monitor prior to use.

Any patient using a prohibited medication/therapy during the course of the study that could interfere with the treatment effect of the study drug or interpretation of the study results may be withdrawn from the study at the discretion of the Investigator and/or Sponsor. However, the Investigator should not withdraw a patient without first confirming it with the Medical Monitor and/or Sponsor. Use of a prohibited medication during the applicable washout period or during the study period will be recorded as a protocol deviation.

8.2.2 Escape Medications

No escape medications are required for this study.

8.2.3 Special Diet or Activities

No special diets or activities are required for this study.

8.3 Examination Procedures

8.3.1 Procedures to be Performed at Each Study Visit with Regard to Study Objective(s)

The following procedures will be performed (see [Appendix 1](#) for description):

Visit 1 (Day -14 ±3)

- Informed consent/Health Information Portability and Accountability Act (HIPAA)
- Demographic data and medical/medication & ocular history
- Urine pregnancy test (for females of childbearing potential)
- [REDACTED] Ocular Discomfort & 4-Symptom Questionnaire
- [REDACTED] Ocular Discomfort Scale
- OSDI
- Best-corrected visual acuity
- Review of qualification criteria
- Slit-lamp biomicroscopy
- Conjunctival redness [REDACTED]
- TFBUT
- Fluorescein staining [REDACTED]
- Lissamine green staining [REDACTED]
- Waiting period of at least 20 minutes

- Run-in solution instillation
 - A trained study technician will instill the first dose of run-in solution (1 drop in each eye) in-office.
- Waiting period of up to 10 minutes following dose of run-in solution
- [REDACTED]
- [REDACTED]
- Slit-lamp biomicroscopy
- Conjunctival redness [REDACTED]
- TFBUT
- Fluorescein staining [REDACTED]
- Lissamine green staining [REDACTED]
- Review of qualification criteria
- AE query
- Patient instillation of run-in solution
 - Qualified patient will self-administer 1 drop of run-in solution in both eyes under study staff observation.
- Run-in solution dispensation
 - Qualified patients will be instructed to instill 1 drop of run-in solution 4 times daily in each eye starting in the evening of Visit 1 and continuing through the morning of Visit 2.
- Dispensation of diaries and patient instructions
 - Qualified patients will also be dispensed a patient daily diary to be completed 4 times daily, and instructed to record each dose of run-in solution taken. Patients will also be instructed to complete the symptom assessments in the morning and in the evening before dosing with run-in solution.
- Schedule patients for Visit 2
 - Qualified patients will be scheduled to return for Visit 2, and will be instructed to instill the morning dose of run-in solution at least 1 hour before the start of Visit 2.

Visit 2 (Day 1)

- Collection and review of run-in vials and patient diaries for qualification and compliance
- Medical/medication & ocular history updates

- AE query
- [REDACTED] Ocular Discomfort & 4-Symptom Questionnaire
- [REDACTED] Ocular Discomfort Scale
- OSDI
- Best-corrected visual acuity
- Review of qualification criteria
- Slit-lamp biomicroscopy
- Conjunctival redness [REDACTED]
- TFBUT
- Fluorescein staining [REDACTED]
- Lissamine green staining [REDACTED]
- Waiting period of at least 20 minutes
- Run-in solution instillation
 - A trained study technician will instill a dose of run-in solution (1 drop in each eye) in-office.
- Waiting period of up to 10 minutes following dose of run-in solution
- [REDACTED]
[REDACTED]
- Slit-lamp biomicroscopy
- Conjunctival redness [REDACTED]
- TFBUT
- Fluorescein staining [REDACTED]
- Lissamine green staining [REDACTED]
- Review of qualification criteria
- Randomization
- Study drug dispensation and instillation
 - Randomized patients will be dispensed 1 treatment kit assigned by IVRS/IWRS, and a trained study technician will instill the first dose of study drug (1 drop in each eye) in-office.
 - Randomized patients will be instructed to instill 1 drop of study drug 4 times daily in each eye starting in the evening of Visit 2 and continuing through the morning of Visit 3.

- Patient daily diary dispensation
 - Randomized patients will also be dispensed a new patient daily diary to be completed 4 times daily, and instructed to record each dose of study drug taken. Patients will also be instructed to complete the symptom assessments in the morning and in the evening before dosing with study drug.
- AE query;
- Schedule patients for Visit 3
 - Randomized patients will be scheduled to return for Visit 3 and will be instructed to instill the morning dose of study drug at least 1 hour before the start of Visit 3.

Visit 3 (Day 8 ± 2): 1-Week Follow-Up

- Collection and review of study drug and patient diaries for compliance
- Medical/medication & ocular history updates
- AE query
- [REDACTED] Ocular Discomfort & 4-Symptom Questionnaire
- [REDACTED] Ocular Discomfort Scale
- OSDI
- Best-corrected visual acuity
- Slit-lamp biomicroscopy
- Conjunctival redness [REDACTED]
- TFBUT
- Fluorescein staining [REDACTED]
- Lissamine green staining [REDACTED]
- Study drug dispensation and instillation
 - Patients will not be dispensed new treatment kit at Visit 3, and a trained study technician will instill a dose of study drug (1 drop in each eye) in-office from the kit dispensed at Visit 2.
 - Patients will be instructed to instill 1 drop of study drug 4 times daily in each eye starting in the evening of Visit 3 and continuing through the morning of Visit 4.
- Patient daily diary dispensation
 - Patients will also be dispensed a new patient daily diary to be completed 4 times daily, and instructed to record each dose of study drug taken.

Patients will also be instructed to complete the symptom assessments in the morning and in the evening before dosing with study drug.

- AE query
- Schedule patients for Visit 4
 - Patients will be scheduled to return for Visit 4 and will be instructed to instill the morning dose of study drug at least 1 hour before the start of Visit 4.

Visit 4 (Day 15 ± 2): 2-Week Follow-Up

- Collection and review of study drug and patient diaries for compliance
- Medical/medication & ocular history updates
- AE query
- [REDACTED] Ocular Discomfort & 4-Symptom Questionnaire
- [REDACTED] Ocular Discomfort Scale
- OSDI
- Best-corrected visual acuity
- Slit-lamp biomicroscopy
- Conjunctival redness [REDACTED]
- TFBUT
- Fluorescein staining [REDACTED]
- Lissamine green staining [REDACTED]
- Waiting period of at least 20 minutes
- Study drug instillation
 - A trained study technician will instill a dose of study drug (1 drop in each eye) in-office from returned kit.
- Waiting period of up to 10 minutes following dose of study drug
- [REDACTED]
- [REDACTED]
- Slit-lamp biomicroscopy
- Conjunctival redness [REDACTED]
- TFBUT
- Fluorescein staining [REDACTED]

- Lissamine green staining [REDACTED]
- Study drug dispensation and instillation
 - Patients will be dispensed 1 new treatment kits assigned by IVRS/IWRS, and a trained study technician will instill the first dose of study drug (1 drop in each eye) in-office from a new kit.
 - Patients will be instructed to instill 1 drop of study drug 4 times daily in each eye starting in the evening of Visit 4 and continuing through the morning of Visit 5.
- Patient daily diary dispensation
 - Patients will also be dispensed a new patient daily diary to be completed 4 times daily, and instructed to record each dose of study drug taken. Patients will also be instructed to complete the symptom assessments in the morning and in the evening before dosing with study drug.
- AE query
- Schedule patients for Phone Call and Visit 5
 - Patients will be scheduled for a phone call at around week 3 (Day 22 ± 2) and return for Visit 5 and will be instructed to instill the morning dose of study drug at least 1 hour before the start of Visit 5.

Phone Call for Drug Compliance: Day 22 ± 2

- The patient will be contacted by telephone and told the following:
 - Patients will be reminded to continue instilling 1 drop of study drug 4 times daily in each eye; and to complete the symptom assessments before dosing with study drug and to record each dose of study drug taken.
- AE query

Visit 5 (Day 29 ± 2): 4-Week Follow-Up

- Collection and review of study drug and patient diaries for compliance
- Medical/medication & ocular history updates
- AE query
- [REDACTED] Ocular Discomfort & 4-Symptom Questionnaire
- [REDACTED] Ocular Discomfort Scale
- OSDI
- Best-corrected visual acuity
- Slit-lamp biomicroscopy
- Conjunctival redness [REDACTED]

- TFBUT
- Fluorescein staining [REDACTED]
- Lissamine green staining [REDACTED]
- Waiting period of at least 20 minutes
- Study drug instillation
 - A trained study technician will instill a dose of study drug (1 drop in each eye) in-office from returned kit.
- Waiting period of up to 10 minutes following dose of study drug
- [REDACTED]
- [REDACTED]
- Slit-lamp biomicroscopy
- Conjunctival redness [REDACTED]
- TFBUT
- Fluorescein staining [REDACTED]
- Lissamine green staining [REDACTED]
- Study drug dispensation and instillation
 - Patients will be dispensed 2 new treatment kits assigned by IVRS/IWRS, and a trained study technician will instill the first dose of study drug (1 drop in each eye) in-office from a new kit.
 - Patients will be instructed to instill 1 drop of study drug 4 times daily in each eye starting in the evening of Visit 5 and continuing through the morning of Visit 6.
- Patient daily diary dispensation
 - Patients will also be dispensed a new patient daily diary to be completed 4 times daily, and instructed to record each dose of study drug taken. Patients will also be instructed to complete the symptom assessments in the morning and in the evening before dosing with study drug.
- AE query
- Schedule patients for Phone Call and Visit 6

Patients will be scheduled for a phone call at around week 6 (Day 43 ± 2) and return for Visit 6 and will be instructed to instill the morning dose of study drug at least 1 hour before the start of Visit 6.

Phone Call for Drug Compliance: Day 43 ± 2

- The patient will be contacted by telephone and told the following:
 - Patients will be reminded to continue instilling 1 drop of study drug 4 times daily in each eye; and to complete the symptom assessments before dosing with study drug and to record each dose of study drug taken.
- AE query

Visit 6 (Day 57 ± 3): 8-Week Follow-Up

- Collection and review of study drug and patient diaries for compliance
- Medical/medication & ocular history updates
- AE query
- [REDACTED] Ocular Discomfort & 4-Symptom Questionnaire
- [REDACTED] Ocular Discomfort Scale
- OSDI
- Best-corrected visual acuity
- Slit-lamp biomicroscopy
- Conjunctival redness [REDACTED]
- TFBUT
- Fluorescein staining [REDACTED]
- Lissamine green staining [REDACTED]
- Waiting period of at least 20 minutes
- Study drug instillation
 - A trained study technician will instill a dose of study drug (1 drop in each eye) in-office from returned kit.
- Waiting period of up to 10 minutes following dose of study drug.
- [REDACTED]
- [REDACTED]
- Slit-lamp biomicroscopy
- Conjunctival redness [REDACTED]
- TFBUT
- Fluorescein staining [REDACTED]
- Lissamine green staining [REDACTED]
- Study drug dispensation and instillation

- Patients will be dispensed 2 new treatment kits assigned by IVRS/IWRS, and a trained study technician will instill the first dose of study drug (1 drop in each eye) in-office from a new kit.
- Patients will be instructed to instill 1 drop of study drug 4 times daily in each eye starting in the evening of Visit 5 and continuing through the morning of Visit 6.
- Patient daily diary dispensation
 - Patients will also be dispensed a new patient daily diary to be completed 4 times daily, and instructed to record each dose of study drug taken. Patients will also be instructed to complete the symptom assessments in the morning and in the evening before dosing with study drug.
- AE query

Phone Call for Drug Compliance: Day 71 ± 2

- The patient will be contacted by telephone and told the following:
 - Patients will be reminded to continue instilling 1 drop of study drug 4 times daily in each eye; and to complete the symptom assessments before dosing with study drug and to record each dose of study drug taken.
- AE query

Visit 7 (Day 85 ± 3): 12-Week Follow-Up

- Collection and review of study drug and patient diaries for compliance
- Medical/medication & ocular history updates
- AE query
- Urine pregnancy test (for females of childbearing potential)
- [REDACTED] Ocular Discomfort & 4-Symptom Questionnaire
- [REDACTED] Ocular Discomfort Scale
- OSDI
- Best-corrected visual acuity
- Slit-lamp biomicroscopy
- Conjunctival redness [REDACTED]
- TFBUT
- Fluorescein staining [REDACTED]
- Lissamine green staining [REDACTED]
- Waiting period of at least 20 minutes

- Study drug instillation
 - A trained study technician will instill a dose of study drug (1 drop in each eye) in-office from returned kit.
- Waiting period of up to 10 minutes following dose of study drug.
- [REDACTED]
- [REDACTED]
- Slit-lamp biomicroscopy
- Conjunctival redness [REDACTED]
- TFBUT
- Fluorescein staining [REDACTED]
- Lissamine green staining [REDACTED]
- Best-corrected visual acuity
- AE query
- Study exit

Early Termination/Discontinuation

If a patient is discontinued from the study prior to Visit 7, then all safety evaluations and efficacy evaluations that are to be performed at Visit 7 should be performed on the day of discontinuation (early termination) prior to commencement of any alternative dry eye therapy (if at all possible).

8.4 Schedule of Visits, Measurements and Dosing

8.4.1 Scheduled Visits

Refer to [Appendix 1](#) for a schedule of visits and measurements.

8.4.2 Unscheduled Visits

These visits may be performed in order to ensure patient safety. All procedures performed at an unscheduled visit will be recorded in the source documents and on the Unscheduled Visit eCRF pages. Any procedure indicated in the eCRF that is not performed should be indicated as “Not done.”

Evaluations that may be conducted at an Unscheduled Visit include:

- Slit-lamp biomicroscopy;
- Best-corrected visual acuity;
- Pregnancy test;
- Assessment of AEs;

- Assessment of concomitant medications and/or treatments; and
- Any other assessments needed in the judgment of the investigator.

8.5 Compliance with Protocol

Patients will be instructed on proper use of the patient daily diary and proper instillation and storage of study drug at the end of Visits 1, 2, 3, 4, 5, and 6, and given written instructions. The patient daily diaries and used and unused study drug vials will be collected at each visit from Visit 2 up to and including Visit 7 to assess dosing and symptom assessment compliance. Dosing compliance will be based off of the used and unused vial count. If the patient is less than 75% or more than 125% compliant with dosing based on the expected number of used vials, then the patient will be deemed non-compliant and a deviation should be recorded.

In the patient daily diary, if more than 25% of Dose Taken boxes are checked “no”, left blank, or missing for a diary period, a patient will be deemed non-compliant and a diary deviation will be recorded. If more than 25% of the total diary symptom assessments for that dosing period are missed, these patients will be deemed non-compliant and a diary symptom assessment deviation will be recorded. These guidelines will be used by the Investigator for determining the patient’s necessary compliance for the study and for recording deviations from this compliance.

8.6 Patient Disposition

8.6.1 Completed Patients

A completed patient is one who has not been discontinued from the study and has successfully completed Visit 7.

8.6.2 Discontinued Patients

Patients may be discontinued prior to their completion of the study due to:

- AE
- Protocol violation
- Administrative reasons (eg, inability to continue)
- Lack of efficacy
- Lost to follow-up
- Pregnancy
- Sponsor termination of study
- Other

Note: In addition, any patient may be discontinued for any sound medical reason.

Notification of a patient discontinuation and the reason for discontinuation will be made to [REDACTED] and/or Sponsor and will be clearly documented on the patient’s source documents and eCRF.

8.7 Study Termination

The study may be stopped at any time by the investigator, the Sponsor, and/or [REDACTED] with appropriate notification.

8.8 Study Duration

An individual patient's participation will involve 7 visits over approximately a 14-week period (98 days).

8.9 Monitoring and Quality Assurance

During the course of the study a monitor, sponsor, or designee, will make routine site visits to review protocol compliance, assess study drug accountability, patient safety, and ensure the study is being conducted according to the pertinent regulatory requirements. The review of the patients' medical records will be performed in a manner that adequately maintains patient confidentiality. Further details of the study monitoring will be outlined in a monitoring plan.

Regulatory authorities of domestic and foreign agencies, [REDACTED]/sponsor quality assurance and or its designees may carry out on-site inspections and/or audits, which may include source data checks. Therefore direct access to the original source data will be required for inspections and/or audits. All inspections and audits will be carried out giving consideration to data protection as well as patient confidentiality to the extent that local, state, and federal laws apply.

9 ADVERSE EVENTS

9.1 Adverse Event

An AE is defined as any untoward medical occurrence associated with the use of a drug in humans, whether or not the event is considered drug-related. An AE can therefore be any unfavorable and unintended sign (eg, an abnormal laboratory finding), symptom, or disease occurring after the patient started dosing with the study drug, without any judgment about causality. Any pre-existing medical condition that worsens after administration of the study drug will be considered a new AE, but exacerbation of conditions related to the signs and symptoms of dry eye will not be reported as an AE unless they persist and/or result in the discontinuation of the patient.

Any medical condition present prior to the administration of the study drug that remains unchanged or improved should not be recorded as an AE at subsequent visits.

AEs (both elicited and observed) and SAEs will be monitored throughout the study. The investigator will promptly review all AEs (both elicited and observed) for accuracy and completeness. All AEs will be documented on the appropriate source document and eCRF.

A worsening in best-corrected visual acuity from Visit 1 [REDACTED] of greater than or equal to 0.22 logMAR units is considered an AE.

Pregnancy is not to be considered an AE, but it is an important medical event that must be followed up as described in [Section 10](#).

Documentation regarding the AE should be made as to the nature, date of onset, end date, severity, relationship to study drug, action(s) taken, seriousness, and outcome of any sign or symptom observed by the physician or reported by the patient upon indirect questioning.

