in the study eye at Day 28. The majority of AEs were mild in severity and no AEs were severe. No serious adverse events (SAEs) were reported. The most frequently reported ocular TEAE and non-ocular TEAE were instillation site pain (20 [16.4%] patients in the 0.3% SI-614 group and 16 [13.6%] patients in the placebo group) and nosopharyngitis (4 [3.3%] patients in the 0.3% SI-614 group and 3 [2.5%] patients in the placebo group). Four TEAEs led to the premature discontinuation of 2 patients; 1 patient in the 0.3% SI-614 group (conjunctivitis right eye, conjunctivitis left eye) and 1 patient in the placebo group (conjunctivitis right eye, conjunctivitis left eye). No safety concerns were raised in terms of visual acuity and slit lamp biomicroscopy assessments.

Potential Risks: Based on the results of Phase 2 and Phase 2/3 studies with SI-614, the most likely AEs that patients may experience include instillation site reactions, and, possibly but less likely, reduced visual acuity. AEs reported in published safety data from clinical trials of HA ophthalmic solutions in dry eye patients included worsening of dry eye symptoms, eye pain, or foreign body sensation. Additionally, based on results from animal studies with SI-614, patients may also experience discharge and redness of the eye.

Potential Benefits: Patients may experience a reduction in various signs and symptoms of dry eye.

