15.1 Adverse Events

An AE is defined as any untoward medical occurrence associated with the use of a drug in humans, whether or not the event is considered drug-related. An AE can therefore be any unfavorable and unintended sign (e.g., an abnormal laboratory finding), symptom, or disease occurring after the patient started dosing with the study drug, without any judgment about causality. Any pre-existing medical condition that worsens after first administration of the study drug will also be considered a new AE. The AE reporting period ends upon study exit. Study drug includes the investigational drug under evaluation and any comparator drug, vehicle,

or any other medications required by the protocol given during any stage of the study. All AEs will be coded using MedDRA Version 25.0.

Treatment-emergent adverse events (TEAEs) are defined as any event that occurs or worsens after the first dose of randomized study treatment.

Severity of an AE is defined as a qualitative assessment of the degree of intensity of an AE as determined by the Investigator or reported to them by the patient. The assessment of severity is made irrespective of relationship to study drug or seriousness of the event and should be evaluated according to the following scale:

- *Mild*: Event is noticeable to the subject, but is easily tolerated and does not interfere with the subject's daily activities.
- *Moderate*: Event is bothersome, possibly requiring additional therapy, and may interfere with the subject's daily activities.
- *Severe*: Event is intolerable, necessitates additional therapy or alteration of therapy, and interferes with the subject's daily activities.

The relationship of each AE to the study drug should be determined by the Investigator using these explanations:

- *Suspected*: A reasonable possibility exists that the study drug caused the AE.
- *Not Suspected*: A reasonable possibility does not exist that the study drug caused the AE.

An overall summary will be presented that includes the number of events and the number and percentage of patients who experienced at least one TEAE, as well as breakdowns of TEAEs further categorized by ocular and non-ocular, severity, relationship to study drug, seriousness and reasons for seriousness, and the number of patients with TEAEs causing premature treatment discontinuation.

In addition to the overall AE summary, summaries will be provided for the following categories of AEs:

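### Protocol 9.1 keeps transient dry-eye exacerbations out of AE reporting while SAP 15.1 defines them as AEs, so the TEAE tables will omit events their own definition covers

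*Protocol*

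**What the plan says.** Protocol Section 9.1 starts from a general rule: "Any pre-existing medical condition that worsens after administration of the study drug will be considered a new AE". The same sentence then makes an exception for the disease under study: "exacerbation of conditions related to the signs and symptoms of dry eye will not be reported as an AE unless they persist". The exception has two limits, because the events are exempt only "unless they persist and/or result in the discontinuation of the patient". The section gives no duration, number of visits or severity that would count as persisting.

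SAP Section 15.1 repeats the general rule without the exception: "Any pre-existing medical condition that worsens after first administration of the study drug will also be considered a new AE". It defines a TEAE as "any event that occurs or worsens after the first dose of randomized study treatment", which matches Protocol Section 11.4.7 in substance.

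Under Potential Risks, Protocol Section 1.1 notes that "AEs reported in published safety data from clinical trials of HA ophthalmic solutions in dry eye patients included worsening of dry eye symptoms", together with eye pain and foreign body sensation. From animal studies with SI-614 it adds that "patients may also experience discharge and redness of the eye".

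For ocular safety assessments, Protocol Section 11.4.7 plans a summary of the shift from baseline to the worst value on treatment. SAP Section 15.3 provides slit-lamp shift tables that compare each follow-up visit with baseline. The SAP's table list contains no worst-value shift.

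**The concern.** The trial's objective covers safety as well as efficacy. A reader of the clinical study report will take the TEAE tables to follow the SAP definition, under which a worsened pre-existing condition is an AE. If transient dry-eye exacerbations are missing because sites were told not to report them, few or no such rows will look like evidence that they were rare.

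Two features add to this. First, the boundary is left to each site. The diary symptoms in SAP Section 4.2 include ocular discomfort, burning and stinging, which overlap with instillation site reactions. One investigator could report stinging as an AE while another treats it as exempt. Second, the causality guidance in Protocol Section 9.1.2 accepts, as evidence of a drug effect, an aggregate finding that known consequences of the underlying disease occur more often on drug. Exempt exacerbations are events of that kind, and they are absent from the AE data on which such a comparison would be made.

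**Working it through.** The point rests on text, so the passages are set side by side.

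**1. Which rule governs the data.** SAP Section 1 gives the SAP precedence over the protocol for statistical analysis methods. It does not claim precedence over what sites record. Recording therefore follows Protocol Section 9.1, and the SAP can tabulate only what was recorded.

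**2. What reaches the TEAE tables.**

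| Dry-eye exacerbation after the first randomized dose | Protocol 9.1 | SAP 15.1 definition | In TEAE tables |
|---|---|---|---|
| Persists | Reported | AE | Yes |
| Leads to discontinuation, persisting or not | Reported | AE | Yes |
| Neither persists nor leads to discontinuation | Not reported | AE | No |

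The two documents disagree only in the third row.

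**3. Whether the third row is a listed risk.** Protocol Section 1.1 lists worsening of dry-eye symptoms and redness, but not from human data on SI-614. The symptom item comes from trials of other hyaluronate solutions, and redness comes from animal work. For SI-614 itself, the section gives instillation site reactions as the most likely AEs, with reduced visual acuity possible but less likely.

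**4. Where else a transient worsening could appear.**
- *Staining and redness scores:* compared by ANCOVA, t-test and Wilcoxon test (SAP Sections 14.1 and 14.3). Descriptive summaries include the minimum and maximum (SAP Section 9.4). No table counts patients who worsened.
- *Diary:* bedtime ocular discomfort and dryness are modelled by day for Days 1 to 14 (SAP Section 14.2.1). The exploratory analyses use weekly averages at Weeks 1, 2, 4, 8 and 12 (SAP Section 14.3.5). A flare of a day or two is averaged within its week, and one in a week outside those five appears only in a listing.
- *Slit lamp:* cornea, conjunctiva and lid are among the structures tabulated as patient counts in three grades, by visit, time point and eye, with shifts from baseline (SAP Sections 4.4 and 15.3). This is real cover, but coarse and visit by visit.
- *Visual acuity:* a loss of at least 0.22 logMAR from Visit 1 is an AE (Protocol Section 9.1). This covers one consequence only.

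**5. Size.** Let *N* be the patients per arm (115 planned), *p* the proportion with at least one exacerbation, and *s* the share of those patients whose exacerbation is reportable under Section 9.1.
- Patients shown in the TEAE tables = *N* × *p* × *s*.
- Patients omitted = *N* × *p* × (1 − *s*).
- If *s* is the same in both arms, the difference in proportions shown is *s* × (*p*₁ − *p*₀), which is the true difference shrunk by the factor *s*.

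The documents give neither *p* nor *s*. The loss could be nil (*s* = 1) or complete (*s* = 0), so no figure can be put on it.

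**The case against.** The strongest case on the other side is that Section 9.1 states a deliberate and common choice. Fluctuation of the disease under study is left to the scheduled scores, and only what persists or ends participation is reported as an AE. On this view SAP 15.1 is an abbreviated restatement with a clause missing. SAP Section 18 lists changes to analyses, and the TEAE definition has not changed, so silence there is not a concealed change. That reading of Section 18 is fair. The design choice is also defensible, provided the safety tables disclose it and the scores are examined for harm as well as for mean benefit. The SAP text does not disclose it, and the scores are examined for harm only in part.

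Three stronger readings are tempting, and the documents do not support them.
- A reader might infer that the TEAE tables cannot show worsening of dry eye at all. They can, for exacerbations that persist or lead to discontinuation.
- A reader might infer that no planned output counts patients who got worse. The slit-lamp counts and shift tables do so for graded findings, and the acuity rule turns a defined loss into an AE. Individual scores are also listed.
- A reader might infer that worsening of symptoms is an established effect of SI-614. Section 1.1 does not say so, and it reports significant symptom improvement over placebo in the Phase 2/3 study.

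A further objection is that any count of patients who worsened will be dominated by ordinary fluctuation. That stands as a limit on the fix. The comparison is between randomized, masked arms, so it remains interpretable as a difference.

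**Conclusion.** The contradiction holds and is narrow. For dry-eye exacerbations that neither persist nor lead to discontinuation, the SAP defines an AE that the protocol tells sites not to report. The TEAE tables will omit these events under a definition that says they are counted. They belong to a category listed under Potential Risks, although the evidence comes from other hyaluronate products and from animals. Other planned outputs give partial cover.

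No magnitude can be stated, because the documents contain no exacerbation rate and no basis for the share that would be reportable. The conclusion assumes that sites followed Section 9.1 as written. It does not touch the primary or secondary efficacy analysis. This is a worthwhile, inexpensive correction to the safety reporting and does not threaten the trial's main conclusion.

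**What to change.** 1. **Reconcile the definitions.** Bring SAP Section 15.1 into line with Protocol Section 9.1, so that the stated AE definition matches what sites record.
2. **Footnote the TEAE tables.** Say that dry-eye exacerbations that neither persisted nor led to discontinuation are not included, and that persistence had no fixed definition.
3. **Add one by-arm Safety-population table** of shift from baseline to worst post-baseline value for conjunctival redness, corneal staining (time-point matched), and diary ocular discomfort and dryness. Use the daily diary scores, because weekly averages dilute a short flare. Show the full shift distribution, or cut-offs fixed before unmasking. This extends to these scores the worst on-treatment summary that Protocol Section 11.4.7 plans for ocular safety assessments.

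The cost is SAP wording, footnotes and one table from data already collected. There are three limits. Ordinary fluctuation is counted in both arms. Flares between visits are visible only in the diary. The diary baseline is an average over Days −7 to −1, so the worst single day will tend to exceed it in either arm, and the table should be read as a comparison between arms and not as an absolute rate of harm.
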